4.1 Screening Log Data

Subject eligibility criteria (including both inclusion and exclusion criteria) and date of informed consent will be listed for all the subjects screened. Note that date of informed consent will be included in the subject disposition listing.

4.2 Disposition and Withdrawals

The number of subject enrolled and the number and percentage of subjects completed and discontinued together with the reasons for discontinuation will be summarized for FAS. The number and percentage of subjects included, and reasons for exclusion, from each of the analysis sets will be presented as well.

Subject disposition (including date of and reasons for early discontinuation from study) will be listed for the FAS.

5. Demographics and Other Baseline Characteristics

5.1 Demographics

All subject demographic and baseline characteristic data will be summarized using descriptive statistics for the full analysis population and/or the evaluable population whenever appropriate.

Age (years) captured at screening visit will be summarized as a continuous variable. Other continuous variables to be presented include weight, height and body mass index.

Categorical or ordinal variables to be presented include sex, race, AJFRS on right and left sides, and Fitzpatrick skin type.

All demographic data will be listed.

5.2 Prior Medications and Therapies

Prior medications/therapies are defined as any medication/therapy which is administered any time prior to the first BELKYRA treatment at Visit 2.1 (Day 0) regardless of when the medication stops.

Partial or missing medication start dates will be handled as per Section 3.3.3 of the SAP.

Prior medications/therapies will be coded by the Anatomical Therapeutic Chemical (ATC) classification system according to the latest World Health Organization (WHO) Drug Dictionary Enhanced WHODDE. Medications/therapies will be summarized by ATC class (level 2) and subclass preferred term (PT) for all patients in the safety population.

Summary tables will show the frequency count and percentage of patients with at least 1 usage of medication/therapy on the subclass level within each ATC class, sorted alphabetically. Percentages will be calculated using the number of patients in the safety population as the denominator.

All prior medications/therapies will be listed.

5.3 Concomitant Medications and Therapies

Concomitant medication/therapy is defined as any medication/therapy which is administered any time on or after the initial BELKYRA treatment at Day 0, regardless of when the medication starts or stops. An episode of medication can be classified into both of prior and concomitant medication/therapy based on how the start and stop date of the medication are relative to the first BELKYRA treatment visit.

Partial or missing medication start and end dates will be handled as per Section 3.3.3.

Any concomitant medication will be recorded collected at each visit, including the medication name, dose, unit, frequency, route of administration, indication, and medication start and end dates.

Concomitant medications/therapies will be coded by the ATC classification system according to the latest WHODDE. Medications will be summarized by ATC class (level 2) and subclass (PT) for all subjects in the safety population.

Summary tables will show the frequency count and percentage of patients with at least 1 usage of medication on the subclass level within each ATC class, sorted alphabetically. Percentages will be calculated using the number of patients in the safety population as the denominator.

All concomitant medications/therapies will be listed.

5.4 Medical History

Descriptions of medical history findings will be coded using latest Medical Dictionary for Regulatory Activities (MedDRA). Medical history will be summarized for the safety population by the number and percentage of patients within each system organ class (SOC) and PT, sorted descending by overall frequency.

Medical history will be listed for all patients in the safety population. Medical history data listings will be sorted by patient number, start date, SOC, PT and verbatim term.

6. Efficacy Analyses

For this post-marketing study, efficacy data are collected at three critical time points, namely, Baseline (prior to Visit 2.1/Day 0), Visit 4 (end of BELKYRA treatment, prior to VOLUMA treatment), and final study visit (Exit Visit 6; end of VOLUMA treatment). The three critical time points will be referenced in most of the statistical analyses for this study. [REDACTED]

Efficacy analyses will be conducted to evaluate the combined effectiveness of sequential treatments with BELKYRA and Juvéderm VOLUMA on the following parameters: Allergan Loss of Jawline Definition Scale (ALJDS), CR (Clinician-Reported) and PR (Patient reported) Submental Fat Rating Scale (SMFRS) scores, Submental Skin Laxity Grade (SMSLG) score, FACE-Q™ satisfaction with lower face and jawline score; FACE-Q™ appraisal of neck; and FACE-Q™ appraisal of area under chin, and investigator and subject [REDACTED]

Efficacy analyses to evaluate the effect of BELKYRA treatment will be conducted at

- Visit 4 (after last BELKYRA treatment) from baseline on ALJDS score, SMSLG score, FACE-Q™ satisfaction with lower face and jawline score; FACE-Q™ appraisal of neck score; FACE-Q™ appraisal of area under chin score.
- Visit 2.x (after each treatment of BELKYRA) from baseline on CR and PR SMFRS scores;
- Visit B2 (after the last BELKYRA treatment) from Visit B1 (before the first BELKYRA treatment) for histological changes in the submental tissue

[REDACTED]

All efficacy analyses will be based on the evaluable population (for combined effectiveness assessments); and on the full analysis population (for BELKYRA treatment evaluation).

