3.2 BELKYRA® TREATMENT

Subjects will undergo treatment with BELKYRA® injected into subcutaneous fat tissue in the submental area (Visit 2.1/Day 0) (note: Screening and Visit 2.1/Day 0 may occur the same day if all eligibility criteria are confirmed prior to treatment and the subject is not participating in the Biopsy Sub-study). Seven days after the initial BELKYRA® treatment (Visit 3.1), the subject will return to the clinic for a safety evaluation. Eight weeks after BELKYRA® treatment, the submental profile will be evaluated by the Investigator and subject. If the Investigator and subject agree that no further intervention is required to achieve the desired result, subjects may receive VOLUMA™ treatment (Visit 4). If further intervention is required to achieve the desired result, subjects may receive up to 5 optional BELKYRA® treatments (Visits 2.2 to 2.6). Optional BELKYRA® treatments will be

Clinical Study Protocol: CMO-MA-FAS-0513

administered at least 8 weeks apart, for a maximum of 6 treatments (including initial BELKYRA® treatment at Visit 2.1/Day 0). Subjects who receive optional BELKYRA® treatments will be contacted by telephone 7 days after each treatment for safety evaluation (Visits 3.2 to 3.6). Eight weeks after each BELKYRA® treatment, the submental profile will be assessed, as described above, and a decision made whether further BELKYRA® treatments are desired. When it is determined that further BELKYRA® intervention is not required or the maximum number (6) of BELKYRA® treatments have been administered, the subject receives VOLUMA™ treatment (Visit 4).

NOTE: Subjects participating in the Biopsy Sub-study will have an additional visit (Visit B2) between the final BELKYRA® treatment and the first VOLUMA™ treatment. See *Figure 3.1* and *Section 3.1: Biopsy Sub-Study*.

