3.3 VOLUMA™ TREATMENT

The initial VOLUMA™ treatment will occur at Visit 4, either 8 weeks after the final BELKYRA® treatment or, if the subject is participating in the Biopsy Sub-study, after the biopsy site has healed. Fourteen days after initial VOLUMA™ treatment, subjects will return to the clinic and the Investigator and subject will assess whether a VOLUMA™ Touch-up treatment is to be performed (Visit 5). The optional Touch-up treatment will occur at Visit 5. All subjects will attend a final Exit Visit 4 weeks after the last VOLUMA™ treatment (Visit 6).

NOTE: If the Investigator and the subject agree that following BELKYRA® treatment, VOLUMA™ treatment is no longer desired or necessary, the subject may exit the study at this time. The subject will be considered as an early discontinuation, and procedures for Visit 6 (Exit Visit) will be performed instead of Visit 4 procedures.

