6.1 Collection of Efficacy Measurements and Derivation of Efficacy Variables

The following measurements and variables are of the efficacy interests. Data on Submental convexity or fullness and Jawline contour assessments, including ALJDS (investigator and independent reviewer), CR-SMFRS, PR-SMFRS, SMSLG and FACE-Q™ Satisfaction with lower face and jawline score/Appraisal of Neck/Appraisal of Area under Chin are collected at baseline (Visit 2.1/Day 0), Visit 4 (end of BELKYRA treatment, prior to VOLUMA treatment), and final study visit (Visit 6; end of VOLUMA treatment). [REDACTED]

- [REDACTED].
- Measurement: ALJDS by investigator and by independent reviewer;
Variables: Change on ALJDS from baseline (numeric variable on the value of right side; and value of left side); and having had at least 1-point improvement from baseline (binary variable). Improvement is defined as having had negative change from baseline.
 - Measurement: CR-SMFRS;
Variables: Change on CR-SMFRS from baseline (numeric variable). Improvement is defined as having had negative change from baseline.
 - Measurement: PR-SMFRS;
Variables: Change on PR-SMFRS from baseline (numeric variable). Improvement is defined as having had negative change from baseline.
 - Measurement: SMSLG;
Variables: Change on SMSLG from baseline (numeric variable). Improvement is defined as having had negative change from baseline.

Statistical Analysis Plan

- Measurement: FACE-Q™ lower face and jawline;
Variables: Change on FACE-Q™ lower face and jawline from baseline (numeric variable on combined scores). Improvement is defined as having had positive change from baseline.
- Measurement: FACE-Q™ Neck;
Variables: Change on FACE-Q™ Neck from baseline (numeric variable on combined scores). Improvement is defined as having had positive change from baseline.
- Measurement: FACE-Q™ Chin;
Variables: Change on FACE-Q™ Chin from baseline (numeric variable on combined scores). Improvement is defined as having had positive change from baseline.

█ [REDACTED]

█ [REDACTED]

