6.2.2.1 Allergan Loss of Jawline Definition Scale (ALJDS)

- Change from baseline to last BELKYRA® treatment on ALJDS
- Change from baseline to final study visit in jawline definition based on Independent Reviewer assessment using the ALJDS and photographic images

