6.2.2.3 Clinician-Reported and Patient-Reported Submental Fat Rating Scale (CR-SMFRS and PR-SMFRS)

Change from baseline to final study visit for CR-SMFRS and PR-SMFRS scores.

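### The Visit 4 BELKYRA results are scored by the two people who decide when BELKYRA stops; name the ALJDS rater and report the Independent Reviewer's Visit 4 rating beside the Investigator's

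*SAP*

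**What the plan says.** **Who stops BELKYRA.** Protocol 3.2 states the cycle: "Eight weeks after each BELKYRA® treatment, the submental profile will be assessed, as described above, and a decision made whether further BELKYRA® treatments are desired". The decision is joint: "If the Investigator and subject agree that no further intervention is required to achieve the desired result, subjects may receive VOLUMA™ treatment (Visit 4". The other route to Visit 4 is that "the maximum number (6) of BELKYRA® treatments have been administered". No numeric stopping criterion is readable.

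**When Visit 4 falls.** Under Protocol 3.3, Visit 4 comes 8 weeks after the last BELKYRA treatment, which is when the decision is made. Biopsy subjects (about 10 of 50) reach it at least 4 weeks after their second biopsy. A subject who, by joint agreement, does not go on to VOLUMA leaves the study, and "procedures for Visit 6 (Exit Visit) will be performed instead of Visit 4 procedures".

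**Who rates.** Under Protocol 7.2, the Investigator scores ALJDS, CR-SMFRS and SMSLG, and the subject scores PR-SMFRS and FACE-Q. An Independent Reviewer scores ALJDS from photographs.

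**What is analysed.** SAP section 6 reads the BELKYRA effect in the Full Analysis Set (FAS) at "Visit 4 (after last BELKYRA treatment) from baseline on ALJDS score, SMSLG score" and on FACE-Q. CR-SMFRS and PR-SMFRS are summarised at each BELKYRA visit and at the three critical visits (SAP 6.2.2.4). Missing values are not imputed (SAP 3.3.2).

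**The independent rating.** SAP 6.1 lists the data held at baseline, Visit 4 and Visit 6, "including ALJDS (investigator and independent reviewer), CR-SMFRS, PR-SMFRS, SMSLG". SAP 6.2.2.1 has an ALJDS change to the end of BELKYRA with no rater named. Its only endpoint naming the reviewer is "Change from baseline to final study visit in jawline definition based on Independent Reviewer assessment using the ALJDS and photographic images".

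**The concern.** A rating made alongside the judgement that ends a course of treatment is not an ordinary follow-up rating. If the rater happens to see the result too favourably, the course ends and that score is kept. If the rater sees it too unfavourably, another treatment and another look follow. With up to six looks, the retained score is selected for favourable error whenever its error is shared with the stopping judgement. This comes on top of ordinary open-label optimism, and a larger sample does not reduce it.

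At stake are the secondary results presented as the effect of BELKYRA alone. No readable text in either document addresses the effect of the stopping rule on them. The plan already holds an ALJDS rating from someone who takes no part in the decision, yet it does not say explicitly that this rating will be analysed at Visit 4.

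**Working it through.** **The plan's own figure.** The only precision figure, in Protocol 10.7, concerns the Visit 6 endpoint: half-width 14.0% with 40 subjects at 78%. It reproduces. The Wald half-width is 1.96 × √(0.78 × 0.22 / 40) = 12.8%; with continuity correction 1/(2 × 40) = 1.25% it is 14.1%. The exact (Clopper-Pearson) half-width is about 13.7%. Enrolment is 40 / 0.80 = 50. Nothing below changes these figures. The documents give no figure for Visit 4.

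**Model.** At look k, let the true improvement be t.
- Stopping judgement = t + e, with e ~ N(0, s²).
- Analysed rating = t + ρe + √(1 − ρ²)·u, with u an independent error of the same SD.
- Independent rating = t + v, with v independent of e and u.
- Scores are rounded to whole grades. Stop at the first look with a judged gain of at least 1 grade, or at look 6.

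Only the cap of six comes from the documents. The values of s, ρ, the gain per treatment and the 1-grade threshold are assumptions.

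**Main set.** s from 0.25 to 0.55 grade; gain 0 to 0.3 grade per treatment; baseline grade 2 or 3, which is the CR-SMFRS entry rule. Excess of the analysed rating over an independent rating of the same subjects at the same visit:

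| ρ | Excess in 1-grade responders | Excess in mean change |
|---|---|---|
| 0 | 0 | 0 |
| 0.2 | about 2–5 points | about 0.02–0.08 grade |
| 0.5 | about 6–14 points | about 0.06–0.2 grade |

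Example with s = 0.4 and gain 0.2: at ρ = 0.2, 59.0% against 54.4% (4.6 points); at ρ = 0.5, 66.9% against 54.4% (12.5 points).

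**Wider set.** s from 0.3 to 0.7; gain 0, 0.2 or 0.35; the improvement itself rounded. At ρ = 0.5 the mean excess is 0.05 to 0.34 grade. The responder excess runs from 9.0 − 4.9 = 4.1 points to 41.2 − 23.9 = 17.3 points. At ρ = 0 it is zero to within simulation error. The independent rating's mean stays on the true value throughout.

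**Dilution by biopsy subjects.** If about 10 of 50 are rated later with fresh error, the pooled excess is 40/50 = 0.8 of the above: 1.6–4.0 points at ρ = 0.2 and 4.8–11.2 points at ρ = 0.5.

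**A force in the other direction.** Subjects who skip VOLUMA have no Visit 4 score. Protocol 10.7 allows 20% for dropout and non-continuation together. As an extreme, suppose all 10 of these skipped VOLUMA as responders and the other 40 responded at 54.4%. The rate over all 50 would be (40 × 0.544 + 10) / 50 = 63.5%, so the observed-case figure would be 9.1 points too low. The net direction is therefore not fixed by the documents.

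**The case against.** **A reader might infer that the reviewer's Visit 4 rating is collected but not analysed.** The documents do not establish this. The end-of-BELKYRA ALJDS endpoint names no rater, SAP 6.1 derives the change and 1-point variables for both raters, the test in SAP 6.2.2.4 has no rater restriction, and SAP section 11 (data collected but not analysed) reads Not Applicable. Parts of SAP section 6 are also blacked out. What stands is that no readable endpoint explicitly assigns that rating an analysis at Visit 4. Protocol 7.2.1 introduces ALJDS as an Investigator assessment, so an unnamed rater would naturally be read as the Investigator.

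**A reader might infer that the Visit 4 result is certainly biased upwards.** That also goes too far. The bias needs shared error, and the decision concerns the submental profile, whereas ALJDS rates jawline contour and SMSLG rates skin laxity. The visit procedures are blacked out, so whether scores are recorded before or after the decision cannot be seen. The cap sends some subjects to Visit 4 without a success judgement. Much larger excesses arise at ρ = 1, but only if the analysed rating is itself the stopping rule, which no readable text says.

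**Other evidence exists.** Image technicians masked to visit measure submental volume and angles (SAP 6.2.3.3), and histology compares biopsies before and after BELKYRA. This stands, but the image results are descriptive, the biopsies cover about 10 subjects, and neither is an ALJDS rating.

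**A reader might extend the point to Visit 6.** The primary endpoint is at Visit 6, after VOLUMA, and no readable text plans a Visit 4 to Visit 6 comparison.

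**Conclusion.** The concern holds as a conditional one. The same two people decide when BELKYRA stops and supply the scores from which its effect is read, and outside the Biopsy Sub-study both happen at Visit 4. Any rating error shared between the two acts inflates the Visit 4 change. Some sharing is plausible, because the same people judge overlapping anatomy. It should be strongest for CR-SMFRS, PR-SMFRS and the FACE-Q area-under-chin module, and weaker for ALJDS and SMSLG.

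The size cannot be derived from the documents. The range of 2 to 14 points for correlations of 0.2 to 0.5 rests wholly on the assumed error, gain and threshold. It was modelled on a CR-SMFRS-type scale; ALJDS entry is grade 2 or above, and FACE-Q runs from 0 to 100, so the grade figures do not transfer directly. Subjects who bypass Visit 4 could offset part or all of it.

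The consequence is confined to secondary BELKYRA-alone results. It is worth acting on because an unconflicted ALJDS rating at Visit 4 is already listed as collected, and because the unnamed rater is an ambiguity in its own right.

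**What to change.** Amend SAP 6.2.2.1 before database lock:

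1. For the ALJDS change to the end of BELKYRA, name the Investigator as rater.
2. Beside it, add the Independent Reviewer's change from baseline to Visit 4 and the proportion improved by at least 1 point, in the FAS on observed cases. Describe this as free of rating error shared with the stopping decision. Do not call it unconditioned on that decision, because the Investigator and subject still choose when Visit 4 occurs. State also whether the reviewer is masked to visit; Protocol 7.2.1 does not say.
3. Report how many FAS subjects had no Visit 4 procedures because they did not go on to VOLUMA. Give a supportive version that includes their end-of-BELKYRA assessment, recorded as Visit 6 procedures.

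The cost is a few lines of SAP text, one added table and a supportive version of it. No new readings are needed, and treatment is unchanged. The limit is that this checks ALJDS only; for the submental scores, the nearest independent evidence is the image analysis already planned.

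A Visit 6 comparison of the submental fat scores is not a remedy. SAP 6.2.2.3 already lists "Change from baseline to final study visit for CR-SMFRS and PR-SMFRS scores", and those scores are taken with VOLUMA in place.

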6.1 Collection of Efficacy Measurements and Derivation of Efficacy Variables

The following measurements and variables are of the efficacy interests. Data on Submental convexity or fullness and Jawline contour assessments, including ALJDS (investigator and independent reviewer), CR-SMFRS, PR-SMFRS, SMSLG and FACE-Q™ Satisfaction with lower face and jawline score/Appraisal of Neck/Appraisal of Area under Chin are collected at baseline (Visit 2.1/Day 0), Visit 4 (end of BELKYRA treatment, prior to VOLUMA treatment), and final study visit (Visit 6; end of VOLUMA treatment). [REDACTED]

- [REDACTED].
- Measurement: ALJDS by investigator and by independent reviewer;
Variables: Change on ALJDS from baseline (numeric variable on the value of right side; and value of left side); and having had at least 1-point improvement from baseline (binary variable). Improvement is defined as having had negative change from baseline.
 - Measurement: CR-SMFRS;
Variables: Change on CR-SMFRS from baseline (numeric variable). Improvement is defined as having had negative change from baseline.
 - Measurement: PR-SMFRS;
Variables: Change on PR-SMFRS from baseline (numeric variable). Improvement is defined as having had negative change from baseline.
 - Measurement: SMSLG;
Variables: Change on SMSLG from baseline (numeric variable). Improvement is defined as having had negative change from baseline.

Statistical Analysis Plan

- Measurement: FACE-Q™ lower face and jawline;
Variables: Change on FACE-Q™ lower face and jawline from baseline (numeric variable on combined scores). Improvement is defined as having had positive change from baseline.
- Measurement: FACE-Q™ Neck;
Variables: Change on FACE-Q™ Neck from baseline (numeric variable on combined scores). Improvement is defined as having had positive change from baseline.
- Measurement: FACE-Q™ Chin;
Variables: Change on FACE-Q™ Chin from baseline (numeric variable on combined scores). Improvement is defined as having had positive change from baseline.

█ [REDACTED]

█ [REDACTED]

6.2 Efficacy Analyses

6.2.1 Primary Efficacy Analysis

The primary endpoint will be the responder rate for jawline improvement on the ALJDS, which is defined as the proportion of subjects who show ≥ 1 -point improvement from baseline on the ALJDS at the final study visit (after last VOLUMA™ treatment received), as assessed by the Investigator. It will be summarized by the number and percentage of subjects together with exact 95% confidence interval. The analysis of primary efficacy endpoint will be based on evaluable population.

6.2.2 Secondary Efficacy Analyses

Secondary efficacy endpoints include followings:

6.2.2.1 Allergan Loss of Jawline Definition Scale (ALJDS)

- Change from baseline to last BELKYRA® treatment on ALJDS
- Change from baseline to final study visit in jawline definition based on Independent Reviewer assessment using the ALJDS and photographic images

6.2.2.2 FACE-Q Questionnaires

- Change from baseline to final study visit on the FACE-Q™ Satisfaction with Lower Face and Jawline module at the final study visit.
- Change from baseline to final study visit on the FACE-Q™ Appraisal of Neck
- Change from baseline to final study visit on the FACE-Q™ Appraisal of Area Under Chin

6.2.2.3 Clinician-Reported and Patient-Reported Submental Fat Rating Scale (CR-SMFRS and PR-SMFRS)

Change from baseline to final study visit for CR-SMFRS and PR-SMFRS scores.

